### **3. STUDY POPULATION**

#### **3.1 Subject enrolment number**

Recruitment will be done by an email which will be disseminated to the student and staff population within NUS. The recruitment notice will be sent out by the NUS Food Science and Technology administrative department via the NUS email and IVLE portal. In addition, validated posters will also be put up within the campus compounds on areas granted for poster pasting as well as on bulletin boards at neighbourhood void decks and community centres within the vicinity of NUH. A targeted fifty middle-aged and older men and women (aged 50 to 75 years, approximately half men and half women) will be recruited with the expectation that  $\geq 40$  subjects ( $\geq 20$  subjects per group) will complete the study ( $\leq 20\%$  dropout rate).

All participants who meet the inclusion criteria stipulated in *Section 3.3* may be enrolled for the study. There will be no restrictions based on gender or race but subjects will need to be adequately equipped with English literacy since the study material provided will be in printed in English only. Research material in other languages is unavailable due to the limitations in capability to translate all the documents effectively.

#### **3.2 Criteria for Recruitment**

Volunteers who responded will be interviewed over the phone by a qualified member of the research team. During the phone interview, the volunteer will be given a brief description of the study design and procedures to be followed. This will also include questions on the eligibility to participate in the research study based on a pre-determined set of criteria. If the volunteer is still interested and eligible, with their verbal approval, arrangements will be made for them come down for the screening visit. If the volunteer does not qualify for the study or declines to participate, these data will be destroyed following the completion of the phone conversation.

#### **3.3 Inclusion Criteria**

1. Ability to give an informed consent
2. Age 50 to 75 years
3. Willing to follow the study procedures

### **3.4 Exclusion Criteria**

All subjects meeting any of the exclusion criteria at baseline will be excluded from participation

1. Significant change in weight ( $\pm 5\%$  body weight) during the past 3 months
2. Allergy to wolfberry
3. Acute illness at the study baseline
4. Exercising vigorously over the past 3 months
5. Consistently following healthy eating pattern diet in the past 3 months
6. Smoking
7. Have an average weekly alcohol intake above 21 units per week (males) and 14 units per week (females): 1 unit = 360 mL of beer; 150 mL of wine; 45 mL of distilled spirits)
8. Pregnant, lactating, or planning pregnancy in the next 6 months
9. Taking dietary supplements which may impact the outcome of interests (e.g. vitamin supplements, antioxidant supplement etc.)
10. Prescribed and taking antihypertensive/cholesterol-lowering/type-2 diabetic medication/ traditional Chinese medicine which started less than 5 years prior to the intervention participation
11. Insufficient venous access to allow the blood collection
12. Exposed to radiation in the last 3 months or expected exposure to radiation in the coming 6 months

\*Defined as having  $> 6$  metabolic equivalents of exercise daily; approximately 20 mins of moderate intensity exercise (e.g. slow jogging) a day for older adults (38).

### **3.5 Withdrawal Criteria**

Subjects are allowed to discontinue participation in the study at any point without giving reasons. Subjects' data will be able to be discarded if they choose to withdraw their participation unless otherwise agreed.

1. If subject is afflicted by an active infection requiring systemic antiviral or antimicrobial therapy that coincides to any of the 6 study visits.
2. Development of allergic reactions during the span of the study
3. Exercising vigorously during the span of the study
4. Smoking during the span of the study
5. Having an average weekly alcohol intake that above 21 units per week (males) and 14 units per week (females): 1 unit = 360 mL of beer; 150 mL of wine; 45 mL of distilled spirits) during the

- span of the study
- 6. Pregnancy during the span of the study
- 7. Starts consuming dietary supplements which may impact the outcome of interest
- 8. Prescribed and taking antihypertensive/cholesterol-lowering/ type-2 diabetic medication
- 9. If subject is not following the prescribed diet
- 10. If a subject develops prolonged stomach or bowel upsets as a result of the intervention

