### **3.6 Subject Replacement**

Subject replacement will not be conducted.

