## **4. TRIAL SCHEDULE**

For this 16-week randomised, parallel-design prospective study, subjects are required to attend 6 visits including an initial screening visit. The duration for each visit is estimated to be approximately 5 hr for the pre- and post-intervention visits and approximately 2 hr for the screening and monthly visits in between. Following the initial screening visit, each visit would be separated by a 4-week interval. The trial schedule is depicted in the schematic attached in Appendix 1.

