### **6.3.2 Study Visits and Procedures**

Prior to each visit, subjects will be required to fast from the night before for approximately 10 to 12 hrs.

The following procedures will be conducted by trained research staff on the pre- and post-

intervention visits:

1. Sampling of fasting-state blood (60 mL) through intravenous cannulation from one of the subject's arms in a room at NUH IMU designated and approved for phlebotomy purposes.
2. Anthropometric measurements including height (pre-intervention visit only), weight and waist circumference at Food Science & Technology Programme, NUS.
3. Blood pressure measurement at Food Science & Technology Programme, NUS.
4. Skin carotenoid status analysis using resonance Raman spectroscopy at Food Science & Technology Programme, NUS.
5. Endothelial-dependent brachial artery FMD and carotid IMT using high-frequency ultrasonographic imaging at the National University Heart Centre
6. Body composition assay by DXA at the Orthopaedic Diagnostic Centre, NUHS
7. Questionnaires and assessment forms including a 3-day food record, Pittsburgh sleep quality index questionnaire, sleep evaluation questionnaire, perceived stress questionnaire, Montreal cognitive assessment, subjective appetite visual analogue scale and quantitative food frequency questionnaire (FFQ: pre-intervention visit only) at Food Science & Technology Programme, NUS.

The following procedures will be conducted by trained research staff on the three visits in between:

1. Sampling of fasting-state blood (20 mL) through intravenous cannulation from one of the subject's arms in a room at NUS OHC designated and approved for phlebotomy purposes.
2. Anthropometric measurements including weight and waist circumference at Food Science & Technology Programme, NUS.
3. Blood pressure measurement at Food Science & Technology Programme, NUS.
4. Skin carotenoid status analysis using resonance Raman Spectroscopy at Food Science & Technology Programme, NUS.
5. Questionnaires and assessment forms including a 3-day food record, Pittsburgh sleep quality index questionnaire and subjective appetite visual analogue scale at Food Science & Technology Programme, NUS.

The collected blood samples will be stored and analysed for the following parameters :

1. Blood lipid-lipoprotein concentrations: Total cholesterol, high-density lipoprotein

cholesterol, low-density lipoprotein cholesterol, and total triglyceride (every 4 weeks).

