2. Blood carotenoid concentration: Fasting state lutein, zeaxanthin, lycopene,  $\alpha$ -carotene,  $\beta$ -carotene,  $\alpha$ -cryptoxanthin, and  $\beta$ -cryptoxanthin concentrations using high-performance liquid chromatography (HPLC; pre- and post-intervention only).
3. Oxidative stress and inflammatory-related parameters: Concentrations of plasma oxidative stress (malondialdehyde (MDA), glutathione peroxidase (GPX), and superoxide dismutase (SOD)) and inflammatory (tumour necrosis factor- $\alpha$ , interleukin-6, monocyte chemoattractant protein-1) biomarkers using commercially available ELISA assay kits (pre- and post-intervention only).
4. Concentrations of vasodilation and vasoconstriction-related biomarkers: nitric oxide, endothelial nitric oxide synthase, and endothelin-1 using commercially available ELISA assay kits (pre- and post-intervention only).
5. Endothelial progenitor cells will be analyzed and enumerated using flow cytometry.
6. Lipidomic profiles: The main classes of glycerophospholipids (phosphatidylcholine, phosphatidylserine, phosphatidylglycerol, phosphatidylinositol, phosphatidylserine, including lysoglycerophospholipids) and sphingolipids (sphingomyelin and ceramides) will be analysed at pre- and post-intervention by high-performance liquid chromatography couple with targeted MRM analysis on triple-quadrupole mass spectrometers (pre- and post-intervention only).
7. Additional plasma will be stored for possible further analyses.

At the end of the subject's first visit, they will also be randomised into either the intervention or control arm using SAS 9.4 software although the intervention will only begin the following week.

One-to-one dietary counselling for each subject and an instruction sheet "My Healthy Plate dietary guide" will be provided by a research dietitian and trained research staff to achieve the healthy eating pattern diet while only subjects in the wolfberry intervention group will receive a provision of 500 g dried wolfberries every 4 weeks along with specific instructions to cook and consume 15 g/day wolfberry as part of a mixed-meal. Compliance with the diet interventions will be promoted by frequent online and in-person contact, 3-day food records (every 4 weeks) as well as photographs of the subject's meals which will be sent to the study personnel for regular checks on pre-determined dates.

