### **6.3.4 Discontinuation Visit and Procedures**

Subjects who voluntary withdraw during the 16-week intervention will not be replaced and the monetary stipend will be pro-rated according to the point in which they decided to withdraw during the study. No follow-up evaluations are required for subjects who withdraw from the study. However, if withdrawal is attributed to an illness or injury afflicted due to the subject's involvement in the study, NUS will be responsible for all compensations.

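### A treated infection that falls on a visit is a withdrawal criterion, with no later outcome collection or rebooking described, so randomised subjects can lose the Visit 5 endothelial outcome avoidably

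*Combined protocol and SAP*

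**What the plan says.** **The criterion.** Section 3.5, item 1, reads: "If subject is afflicted by an active infection requiring systemic antiviral or antimicrobial therapy that coincides to any of the 6 study visits". No reason is given, and the section does not separate stopping the intervention from leaving the study. Items 2 to 6 of the list apply throughout the study; item 1 is the only one tied to visit dates.

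**After withdrawal.** Section 6.3.4 states: "No follow-up evaluations are required for subjects who withdraw from the study". Section 3.6 states: "Subject replacement will not be conducted".

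**Visits.** Section 4 states that "subjects are required to attend 6 visits including an initial screening visit" and that after screening "each visit would be separated by a 4-week interval". It gives no tolerance around the visit dates. Section 6.3.2 places randomisation after the first set of measurements: "At the end of the subject's first visit, they will also be randomised into either the intervention or control arm".

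**Measurements.** Section 6.3.2 schedules FMD, carotid IMT and DXA at the first and last study visits (Visits 1 and 5). The oxidative-stress and inflammatory panel has the same timing: "monocyte chemoattractant protein-1) biomarkers using commercially available ELISA assay kits (pre- and post-intervention only". So do blood carotenoids, the vasoactive markers and lipidomics. Visits 2 to 4 have weight, waist, blood pressure, skin carotenoids, food records, sleep and appetite forms, and a lipid panel: "cholesterol, low-density lipoprotein cholesterol, and total triglyceride (every 4 weeks". Endothelial progenitor cells (EPC) are listed without a visit.

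**Analysis.** Section 11.1 names endothelial function as the primary outcome. Section 11.2 specifies repeated-measures ANOVA and states no analysis set or missing-data method.

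**The concern.** Item 1 depends on a coincidence of dates. A treated infection between two visits has no consequence under it, while the same infection on a visit date meets a withdrawal criterion. Because no later evaluation is required and nobody is replaced, the plain reading is that a passing illness at an intermediate visit also removes the Visit 5 FMD and IMT, which would be read weeks later. At Visit 5 itself the outcome is lost because the text describes no way to take the measurement on another day.

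At stake is the number of subjects with a final endothelial measurement, in a trial that recruits 50 and needs at least 40 completers. Section 11.1 says that endothelial function was not powered and that its results will supply effect sizes for later research. The precision of those estimates is therefore the main thing this outcome can deliver.

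**Working it through.** **1. The plan's own figure.** Section 3.1 recruits 50 and expects at least 40 completers with at most 20% dropout. Check: 40 / (1 − 0.20) = 50, which reproduces it. The allowance is 50 − 40 = 10 subjects.

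**2. Visits that count.** Six visits are screening plus Visits 1 to 5. Randomisation comes at the end of Visit 1, so four visits (2 to 5) fall wholly after it. Three of these are intermediate.

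**3. Expected losses.** The documents give no rate of treated infection. Assume a probability p per visit, the same at each visit and independent across visits, with p from 0.5% to 5%.

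- Lost over Visits 2 to 5: 50 × (1 − (1 − p)^4)
- Of these, triggered at Visits 2 to 4: 50 × (1 − (1 − p)^3)
- Lost if only Visit 5 counted: 50 × p

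| p | Visits 2–5 | of which Visits 2–4 | Visit 5 only | Visits 2–5 as share of the 10 |
|---|---|---|---|---|
| 0.5% | 0.99 | 0.75 | 0.25 | 10% |
| 1% | 1.97 | 1.49 | 0.50 | 20% |
| 2% | 3.88 | 2.94 | 1.00 | 39% |
| 3% | 5.74 | 4.37 | 1.50 | 57% |
| 5% | 9.27 | 7.13 | 2.50 | 93% |

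The Visits 2–4 share is 1.49 / 1.97 = 76% at p = 1% and 7.13 / 9.27 = 77% at p = 5%, so about three quarters throughout.

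**4. Effect on precision.** The standard error of a difference between two equal groups varies as 1/√n per group. Take the worst case, in which other dropout already uses the whole allowance and these losses come on top of it:

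- 2 lost (20 to 19 per group): √(20/19) = 1.026, a standard error 2.6% larger
- 6 lost (20 to 17): √(20/17) = 1.085, or 8.5% larger
- 9 lost (20 to 15.5 on average): √(20/15.5) = 1.136, or 13.6% larger

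If the losses fall within the allowance, at least 40 completers remain, but these subjects are still missing from the final comparison.

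**5. What each remedy recovers.** Collecting Visit 5 outcomes after the criterion is met recovers nearly all cases triggered at Visits 2 to 4, about three quarters of the total. It does not give a measurement away from the infection when the infection falls at Visit 5. Rebooking addresses that remaining quarter.

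**The case against.** A strict withdrawal rule is a legitimate design choice, and item 1 does not formally contradict section 6.3.2. The allowance of 10 may already cover such losses, and at the low end of the assumed range only one or two subjects are involved. Those points stand, and they limit the size of the concern.

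A reader might also infer more than the text supports:

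- **That no infection-sensitive endpoint is read at Visits 2 to 4.** Lipids and blood pressure are read there, EPC has no stated timing, and the documents classify no endpoint by sensitivity to infection. What can be said is that no FMD, IMT, inflammatory, oxidative-stress or vasoactive measurement is scheduled then.
- **That the rule exists only to protect measurements.** The link to visit dates suggests this, but no reason is given, and the same list contains criteria about subject welfare.
- **That withdrawal is permanent and rebooking is forbidden.** This is read from silence. Section 3.5 has no operative statement that a subject meeting a criterion must leave. For persistent gut symptoms, sections 2.3.2 and 9.3 leave stopping to the investigators' judgement, while item 10 lists prolonged symptoms as a criterion. The schedule in Appendix 1 and the visit checklists in Appendices 2a to 2d are not in the available text and might contain a window.
- **That every one of the six visits can remove a randomised subject.** Screening, and Visit 1 until its end, come before randomisation.
- **That only moving the assessment would help.** Step 5 of the working shows that Visit 5 collection alone recovers most cases.

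What survives is that the available text, followed as written, ends outcome collection over a transient event and offers no route to avoid it.

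**Conclusion.** The concern holds in a limited form. Section 3.5 item 1, read with sections 3.6, 4 and 6.3.4, can cost a randomised subject the final endothelial outcome because of a treated infection at any of Visits 2 to 5. For Visits 2 to 4 this happens although none of the vascular imaging or the inflammatory, oxidative-stress and vasoactive markers is due on that day.

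The size rests entirely on an assumed infection rate: about 1 to 9 of 50 subjects at 0.5% to 5% per visit, and about 2 to 6 at 1% to 3%. This assumes that visits are independent and that staff apply item 1 as an automatic exit.

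The harm is avoidable loss of precision. A reader might suspect bias as well, but nothing in the documents shows that such infections would differ between arms or relate to the outcome. The point merits a change of wording because the remedy is cheap; it does not undermine the design.

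**What to change.** Reconcile section 3.5 item 1 with sections 4, 6.3.2 and 6.3.4, so that meeting item 1 does not by itself end outcome collection. Specifically:

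- State whether item 1 ends participation or affects only the measurement due that day.
- Collect the Visit 5 outcomes from every randomised, consenting subject who meets item 1.
- Allow an affected assessment to be rebooked within a stated window, with its length set by the sponsor. Flag any sample or reading taken during a treated infection.
- Record and report actual exposure time where Visit 5 is moved.
- State the visits at which EPC are measured, and state in section 11.2 the analysis set and missing-data method that apply to these subjects.

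Whether a subject continues the study food, or continues to participate on clinical grounds, stays with the investigators and is not addressed here.

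The cost is protocol wording, an occasional rebooked visit, and a few Visit 5 readings later than planned.

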## **11. SAMPLE SIZE AND STATISTICAL METHODS**

### **11.1 Determination of Sample Size**

Outcomes of interests in this research include the difference in plasma zeaxanthin and MDA concentrations. Previous research reported that the plasma zeaxanthin concentration was significantly increased after consuming 15 g/day of wolfberry for 28 days ( $0.058 \pm 0.011 \mu\text{mol/L}$ , mean  $\pm$  SEM) compared to not consuming wolfberry ( $0.006 \pm 0.003 \mu\text{mol/L}$ , mean  $\pm$  SEM) (31). For the current study, presuming the proposed experiment yields similar results as previously,  $\geq 12$  participants per group will provide  $\geq 95\%$  power at  $\alpha = 0.05$  (two-tailed) to statistically confirm a similar difference. Also, recent research reported that the plasma MDA concentration was decreased after consuming 14 g/day of wolfberry with meal for 45 days ( $-3 \pm 1 \mu\text{mol/mg}$  of protein, mean  $\pm$  SEM) compared to not consuming wolfberry ( $3 \pm 1 \mu\text{mol/mg}$  of protein, mean  $\pm$  SEM) (32). For the current study, presuming the proposed experiment yields similar results as previously,  $\geq 20$  participants per group will provide  $\geq 95\%$  power at  $\alpha = 0.05$  (two-tailed) to statistically confirm a similar difference.

Although the primary outcome of this research is the difference of endothelial function after consuming a healthy eating pattern diet with wolfberry versus a same diet without wolfberry, power calculations based on endothelial function-related parameters were not done due to the lack of preliminary data. As such, the endothelial function-related responses in the current study will be used to calculate effect sizes for future research.

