## **11.2 Statistical and Analytical Plans**

The main effects of meal, time, and their interactions on the dependent variables will be determined by repeated-measures analysis of variance (ANOVA). All analyses will be performed in SAS 9.4 (SAS Institute Inc., Cary, NC) and results will be expressed as mean  $\pm$  SE, otherwise noted, and statistical significance will be accepted at  $p < 0.05$  (two-tailed).

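### Subjects withdrawn for not following the diet need no final FMD or IMT, so that comparison is selected on post-randomisation adherence; keep them to Visit 5 and analyse by assigned arm

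*Combined protocol and SAP*

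**What the plan says.** Section 3.5 lists ten withdrawal criteria. The ninth reads "If subject is not following the prescribed diet". The available text attaches no threshold, time window or decision-maker to it, whereas the alcohol criterion in the same list gives weekly unit limits. Appendices that might hold a rule, such as the visit checklists and the meal photograph sheets, are not reproduced.

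Three other provisions decide what follows from a withdrawal:

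- Section 6.3.4: "No follow-up evaluations are required for subjects who withdraw from the study".
- Section 3.6: "Subject replacement will not be conducted".
- Section 6.3.2 lists "Endothelial-dependent brachial artery FMD and carotid IMT using high-frequency ultrasonographic imaging at the National University Heart Centre" among the procedures of the pre- and post-intervention visits. It is absent from the list for the three visits in between.

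Section 11.1 says that "the primary outcome of this research is the difference of endothelial function after consuming a healthy eating pattern diet with wolfberry" is compared with the same diet without it. Section 11.2 plans a repeated-measures ANOVA with meal, time and their interaction. It names no analysis set, no rule for analysing by assigned arm and no method for missing data.

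**The concern.** Adherence is observed after randomisation, and subjects who stop following a diet may differ from the others in health and motivation. Removing them, and not measuring them, means that FMD and IMT are compared between subgroups whose comparability randomisation no longer guarantees.

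Two features make this worth settling in advance. First, Section 11.1 says that "the endothelial function-related responses in the current study will be used to calculate effect sizes for future research", so a distorted estimate could pass into the planning of the next trial. Second, an analysis of adherent subjects can always be taken from complete data, but final measurements that were never made cannot be recovered.

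**Working it through.** **1. The plan's own figure.** Section 3.1 recruits 50 to leave at least 40 completers (20 per group) at no more than 20% dropout: 40 / (1 − 0.20) = 50. This reproduces. The plan thus allows for losing up to 50 × 0.20 = 10 subjects. It does not say how many might go under criterion 9.

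**2. What a removed subject contributes.** With one value before and one after, the meal-by-time interaction is the between-arm difference in mean change. A subject withdrawn under criterion 9 before Visit 5, with no follow-up evaluation, has no change score. With no missing-data method stated, that subject carries no information on the FMD or IMT comparison. Endothelial progenitor cells are also named as an endothelial marker, but Section 6.3.2 gives no timing for them, so this step covers FMD and IMT only.

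**3. Possible bias under no wolfberry effect.** The documents give no adherence rate and no SD for FMD or IMT, so these are illustrations. Assumed: 25 per arm (no allocation ratio is stated), the *k* least adherent wolfberry subjects and *j* least adherent controls removed, and a correlation *r* between adherence and outcome change for reasons other than wolfberry.

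Normal approximation, in SD units, with φ the normal density and z_q its q-quantile:

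bias = r × [φ(z_q)/(1 − q) at q = k/25, minus the same at q = j/25]

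For k = 5, j = 0: q = 0.20 and φ(z_q)/(1 − q) = 0.350, so the bias is 0.070, 0.105 and 0.175 for r = 0.2, 0.3 and 0.5. Simulation with 40,000 trials per setting and a pooled t test gives slightly smaller values:

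| Removed (wolfberry, control) | Bias in SD, r = 0.2 to 0.5 | Rejection rate of the 5% test |
|---|---|---|
| 5, 0 | 0.07 to 0.17 | 5.6% to 8.8% |
| 3, 0 | 0.05 to 0.11 | 5.2% to 6.8% |
| 5, 2 | 0.04 to 0.09 | not reported |
| 5, 5 | about 0 | not reported |

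For the first row, the standard error of the difference is √(1/20 + 1/25) = 0.30 SD, so even the extreme bias is a little over half a standard error.

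**4. What retention does to the effect and to power.** If the effect is proportional to dose and 5 of 25 ate half the portion, the by-assignment effect is (20 + 5 × 0.5)/25 = 0.90 of the full-dose effect; if they ate none, 20/25 = 0.80.

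With a two-sample t test at two-sided 0.05, the difference detectable at 80% power is 0.91 SD with 20 per arm and 0.81 SD with 25 per arm. Take an assumed full effect of 0.91 SD, and wolfberry-arm non-adherers with zero effect:

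| Non-adherent in wolfberry arm | Power by assigned arm, 25 per arm |
|---|---|
| 0% | 0.88 |
| 5% | 0.85 |
| 10% | 0.81 |
| 20% | 0.71 |

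The comparator is 0.80 with 20 adherent completers per arm, which assumes that the whole dropout allowance is used. Retention therefore costs power only if non-adherence exceeds about 10% in this illustration.

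**The case against.** The strongest reply is that the bias needs unequal removal, and the plan works against that. Only the wolfberry arm is told to "consume 15 g/day wolfberry as part of a mixed-meal", so a reader might infer that criterion 9 falls harder on that arm and tilts the result in favour of wolfberry. The documents do not support that. Section 8.3 blinds study personnel and investigators to assignment, and blinded staff can judge only the My Healthy Plate diet that both arms follow. Unequal removal requires them to learn the arm, for example from meal photographs. That is possible but not shown. With balanced removal the illustrated bias is about zero. This part of the objection stands.

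A reader might also infer that the plan would overstate the effect by a known amount. In the half-dose case, 1/0.90 − 1 = 11%. That figure presumes that the target is the effect of assignment. The hypotheses in Section 2.2 speak of consuming wolfberry, and an effect in consumers is a defensible aim for a food study. But no section declares an adherent-only population, and removing subjects without measuring them does not estimate that effect cleanly either.

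Nor do the documents show that the whole primary outcome is lost, or that criterion 9 is arbitrary in practice. The timing of progenitor cells is not stated, a threshold may sit in an unseen appendix, and any misclassification rate would rest on an invented cut-off.

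Finally, Section 6.3.4 opens with voluntary withdrawal and says that evaluations are not required; it does not forbid them. Still, its sentence on follow-up is general, and nothing else in the text asks for a final visit from subjects whom the team removes. Even a precise threshold would leave that gap.

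**Conclusion.** The point holds as a minor one. Followed as written, Sections 3.5, 6.3.4 and 6.3.2 leave subjects removed under criterion 9 before Visit 5 without a final FMD or IMT, and the comparison in Section 11.2 is then confined to subjects selected partly on adherence after randomisation.

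Any bias is likely small, and the documents do not allow it to be quantified. The zero figure rests on balanced removal and on adherence relating to outcome alike in both arms. The figure of 0.07 to 0.17 SD rests on using the wolfberry arm's full 20% allowance, removing no controls, removing strictly by adherence rank, and a correlation of 0.2 to 0.5. It is an upper illustration, not an estimate. The case for change rests less on that size than on the low cost of the final measurement and the impossibility of obtaining it later.

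**What to change.** - **Section 3.5:** replace criterion 9 with a statement that a subject not following the diet is re-counselled, the lapse is recorded, and the subject stays in the study.
- **Section 6.3.4:** ask every subject who stops the diet, or who meets a non-safety withdrawal criterion (3, 4, 5, 7 or 8, and 9 if any form of it is kept), and who has not withdrawn consent, to attend Visit 5 for FMD, IMT and blood. The other criteria in this list also remove subjects for events after randomisation, so changing criterion 9 alone would leave the same gap. Safety criteria (1, 2, 6 and 10) can still stop the intervention.
- **Section 11.2:** analyse all randomised subjects with outcome data by assigned arm. Any adherent-only result is a labelled sensitivity analysis, with its threshold and data source fixed before unblinding.

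Cost: a few sentences of text. Under the payment table in Section 6.3.3, a subject retained from just after Visit 1 receives 3 × $50 + $300 = $450, so at most 10 × $450 = $4,500 if the whole dropout allowance came from criterion 9. The assessments themselves are extra, but are those already planned for every subject. The estimated effect is diluted, and power falls if many subjects are non-adherent (0.71 against 0.80 in the 20% illustration). Some subjects will decline Visit 5, and those who withdraw consent remain missing.
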